Methods: The study will be conducted over a 3-day period, involving healthy young female adults. The participants will be randomly assigned to seven groups: Control (250 mL of warm water); Coffee Group (2.25g of coffee per 250ml of hot water); Honey-sweetened coffee group (2.25g of coffee per 250 mL of hot water with 20 mL of honey); Black tea group (2g black tea diffused in 250 mL hot water); Honey-sweetened black tea (2g black tea diffused in 250 mL hot water with 20 mL honey; Green Tea group (2g green tea diffused in 250 mL hot water); and Honey-sweetened green tea group (2g green tea diffused in 250 mL hot water with 20 mL honey. The basal measurements of each participant will be taken, after which the participants will be given their designated beverages. The blood pressure and heart rate of each participant will be measured at 15, 30, 45, and 60 minutes, and blood glucose at 30 and 60 minutes after consumption.

Discussion: This research aims to provide significant insights regarding the possible health benefits or risks linked to the consumption of coffee, black tea, green tea and honey-sweetened coffee, black tea, and green tea . It will specifically focus on their effects on critical physiological factors such as blood pressure, heart rate, and blood glucose level. Understanding these factors is essential for maintaining individual health, as any adverse changes in them can lead to detrimental health consequences. By examining the relationship between these beverages and these vital health indicators, the study seeks to contribute to the broader understanding of dietary influences on cardiovascular and metabolic health.

Keywords: Coffee, Black tea, green tea, Honey-sweetened coffee, Honey-sweetened tea, Blood pressure, Heart rate, Blood glucose

Introduction

Coffee and tea stand out as globally favoured and versatile beverages of choice. Their nutritional significance primarily derives from their bioactive constituents. Coffee and tea are enriched with different polyphenols, known for their wide array of biological functions, encompassing antioxidant capabilities, potential cancer prevention, inflammation suppression, and protective properties against conditions like cardiovascular diseases, diabetes, hyperlipidemia, and obesity [1]. The polyphenols in coffee are chlorogenic acid, diterpenes, and trigonellin, while those in tea are catechins [2]. The catechins in green tea are epigallocatechin-3-gallate, gallocatechingallate,

epicatechin, epigallocatechin, gallocatechins, and epicatechin-3-gallate [3]. Those in black tea are theaflavins, amino acids L-theanine, epigallocatechingallate, and thearubigins [4]. Besides the polyphenol constituents, coffee and tea are rich in caffeine. Caffeine is a natural stimulant well-known to stimulate the central nervous system. There are varying quantities of caffeine in coffee and tea. Coffee contains 95-200 mg, black tea 14-70 mg, and green tea 24-45 mg of caffeine [5].

Green tea is known for its potential impact on blood pressure and blood glucose. Several studies have explored the relationship between green tea consumption and blood pressure [6,7]. In addition, green tea has also been associated with glucose metabolism. It has been documented to improve tissue insulin sensitivity [8,9]. Some studies suggest that the consumption of green tea decreases postprandial blood glucose spikes [10,11]. Black tea might have the potential to prevent cardiovascular diseases. Studies have also linked black tea consumption to a reduction in blood pressure and a lower risk of developing hypertension [12,13]. Furthermore, black tea has also been documented to have an impact on blood glucose levels. The consumption of black tea has the potential to lower the risk of developing type 2 diabetes. Black tea and its components have been shown to have the potential to lower blood glucose and reduce the risk of diabetes mellitus [14]. Coffee, as a rich source of caffeine, has been studied for its impact on blood pressure and blood glucose. The consensus among studies is that caffeine can lead to a transient increase in blood pressure due to its stimulatory effects on the central nervous system [15,16]. Additionally, coffee consumption can influence blood glucose levels. Studies have reported that coffee consumption increases blood glucose levels, decreases glucose disposal, and reduces insulin sensitivity [17,18]. While other studies have reported that coffee consumption improves insulin sensitivity, contributes to better blood glucose regulation, and reduces the risk of diabetes mellitus [19,20].

Honey has a rich history of utilisation dating back to ancient times, thanks to its nutritional and therapeutic properties [21]. Honey is produced globally and is primarily composed of carbohydrates, particularly in the form of monosaccharides like fructose and glucose. Honey is enriched with different biological compounds, like flavonoids and other types of antioxidants, which have been suggested to have cardioprotective benefits [22]. It has a lower glycemic index compared to regular sugar, which may result in a slower release of glucose into the bloodstream and potentially have a favourable impact on blood sugar levels [23].

Coffee and tea are either taken plain or sweetened with sugars, such as white sugar or artificial sweeteners. However, the use of natural sweeteners like honey is becoming more and more popular. Research on the possible health impacts of coffee, tea, and honey has been done separately; nevertheless, a significant gap persists in the research regarding the synergistic effects of tea and coffee when sweetened with honey. This study will investigate whether a three-day consumption of coffee and tea sweetened with honey will significantly influence the blood pressure and blood glucose level in healthy young female adults.

Study goals and objectives

Goals

The primary aim of this study is to determine the effect of acute consumption of honey-sweetened coffee, black tea, and green tea on systolic blood pressure, diastolic blood pressure, heart rate, and blood glucose level in healthy female participants.

Objectives

- To determine whether a three-day consumption of honey-sweetened black tea, green tea, and coffee will have an effect on blood pressure in healthy female individuals.
- To determine whether a three-day consumption of honey-sweetened black tea, green tea, and coffee will have an effect on heart rate in healthy female individuals.
- To determine whether a three-day consumption of honey-sweetened black tea, green tea, and coffee will have an effect on blood glucose level in healthy female individuals.

Study design

The study is an experimental study; specifically, it is a randomized controlled trial that will involve healthy young female adults between the ages of 18 and 26 years. The participants will consume honey-sweetened black tea, green tea, and coffee, or plain black tea, green tea, and coffee, or warm water, one cup a day for 3 days. The study will be carried out in the Physiology Laboratory, University of Uyo, and will be done within the period of July to October 2023. Each participant will fill out a consent form prior to the study, after which the participants will be given the beverages and observed for 60 minutes, during which their blood pressure, heart rate, and blood glucose level will be measured. This procedure will be repeated for the 3 days of the study. Prior to the consumption of the beverages, baseline measurements of blood pressure, heart rate, and blood glucose will be taken. For this study, a minimum of 200 volunteers will be recruited, and out of this, the eligible participants will be selected.

Methodology

The randomized controlled trial will be carried out among female students studying at the University of Uyo. The participants will be randomly grouped as follows:

Group 1 (Control) will be given 250 mL of water.

Group 2 (Coffee group) will be given 2.25 g of coffee per 250 mL of hot water.

Group 3 (Honey-sweetened coffee group) will be given 2.25 g of coffee per 250 mL of hot water with 20 mL of honey.

Group 4 (Black tea group) will be given one tea bag (2 g) per cup (250 mL) of hot water.

Group 5 (Honey-sweetened black tea) will be given one tea bag (2 g) per cup (250 mL) of hot water with 20 mL of honey.

Group 6 (Green tea group) will be given one bag (2 g) per cup (250 mL) of hot water.

Group 7 (Honey-sweetened green tea) will be given one bag (2 g) per cup (250 mL) of hot water with 20 mL of honey.

Study procedure

• Participants will be screened for eligibility criteria and will be provided with informed consent to participate in the study.

• The participants will be divided into seven groups, as specified above, through random allocation.

• After arrival, the subjects will be allowed to rest for 30 minutes. Then, baseline measurements of their blood pressures, heart rates, and blood glucose levels will be taken. This will serve as the 0-minute measurement. The subjects will then be given the standardized drinks according to their groups.

• Blood pressures and heart rates of the subjects will be measured and recorded 15 minutes, 30 minutes, 45 minutes, and 60 minutes after consumption of the drinks, while blood glucose levels of the subjects will be measured and recorded 30 minutes and 60 minutes after consumption.

• Blood pressure and heart rate will be measured using a digital sphygmomanometer. Blood pressure is measured in millimeters of mercury (mmHg) and recorded with the systolic number first, followed by the diastolic number. Heart rate is measured in beats per minute (bpm).

• Blood glucose level will be measured with a glucometer. Blood glucose level will be measured in mg/dL.

Intervention

Coffee, black tea, green tea, and honey

The coffee that will be used for this study is Nescafé Gold Blend, manufactured by Nestlé Coffee Brand, Nestlé Global, Vevey, Switzerland. The black tea is Lipton Yellow Label Black Tea, manufactured by Lipton Teas and Infusions, Rotterdam, Netherlands, and the green tea is Qualitea Natural Green Tea, packed by Qualitea Ceylon (PVT) LTD, Wattala, Colombo, Sri Lanka. These will be obtained from Market Square, Ibom Tropicana Mall, Uyo, Akwa-Ibom State, Nigeria. Raw dark amber honey produced by Apis mellifera adansonii will be used for this study, and it will be obtained from Vika Farms located in Mbak Etoi, Akwa-Ibom State, Nigeria.

The participants will be given a cup per day for 3 days. A tea cup will be prepared by infusing a tea bag in 250 mL of hot water (95°C for black tea and 80°C for green tea). The infusion will be done for 7-10 minutes with constant stirring. A cup of coffee will be prepared by dissolving 2.25 g of instant coffee in 250 mL of 95°C water with proper stirring.

The water will be allowed to boil and cooled down to a respectful temperature before the addition of either a tea bag or coffee. The beverages will then be allowed to cool to approximately 35 degrees before honey is added and given for consumption. The control group will be given 250 mL of water at 35°C.

Measurement of blood pressure, heart rate, blood glucose

Blood pressure and heart rate will be recorded on the left arm using an automated blood pressure monitor (Shanghai Little Doctor Electronics CO. LTD, Nantong 226007, China). First, the cuff

will be firmly placed around the arm (biceps). Then the power button will be pressed, and the automatic machine will read the blood pressure through the cuff. The reading will be taken three times, and the average value will be determined.

Blood glucose level will be measured by the oxidase method using a fine test glucometer (Osang HealthCare (Infopia), [name]). Firstly, the fingertip will be cleaned with an alcohol wipe and allowed to dry completely. The glucometer will be turned on, and a test strip will be inserted into the designated slot. A lancing device will be used to gently prick the fingertips of the subjects. The finger will be gently squeezed to help produce a small blood drop. Then the edge of the test strip will be used to touch the blood droplet until the meter beeps or indicates that it has received enough blood. The glucometer will process the blood sample and display the blood glucose level on the screen.

Sample size

The sample size was determined to assess the number of participants required to measure the mean difference between groups. The sample size was calculated using the formula explained by Charan et al. [24].

Sample size = $[2SD^2(1.96 + 0.84)^2] \div d^2$

Where:

SD = standard deviation from previous studies or pilot study

d = effect size- difference between mean values

However, a sample size of 70 will be used in this study based on available funds, equipment, manpower, and data from the literature.

Randomized controlled trial procedures

Recruitment and screening

The recruitment of participants will occur at the University of Uyo, Uyo, Akwa-Ibom State. Specifically, healthy female students studying at the University will be recruited for this study. The recruitment process will involve all the departments within the Town Campus and Annex Campus of the University. The contact details of the class representatives of each level in each department within the aforementioned campuses will be obtained. The recruitment invitation for the study will be posted on the WhatsApp group page of each class by their class representative. In addition, flyers will also be distributed throughout the classrooms and hostels. A referral incentive of N100 per three referrals will be added to the recruitment invitation. The potential participants will be attended to by two experienced and trained research staff who are accustomed to all the study procedures. Participants who meet the preliminary eligibility criteria (living in the university hostel or living in close proximity to the university) and state clear interest in study participation, will then be invited to voluntarily complete the screening questionnaire and informed consent process.

Eligibility, informed consent, and enrollment processes

The participants who meet all the pre-screen requirements will be taken through the enrollment process, which includes eligibility for the study by filling out a questionnaire; filling out and signing the informed consent form; and measurement of their vitals (temperature, pulse rate, respiration, blood glucose level, and blood pressure). All participants that meet all the requirements for this stage will be considered fully enrolled for the study.

Eligibility criteria

Inclusion criteria are as follows:

(1) Age between 18 and 26; (2) Non-habitual coffee and tea drinkers who consume coffee, green tea, or black tea 2-5 times in the last two months; (3) Non-allergic to coffee, green tea, black tea, or honey; (4) Absence of medication use; (5) Will refrain from ingesting energy drinks, carbonated beverages, caffeinated beverages, or food for 24 hours before the study and throughout the study periods; (6) Will not consume anything except water after 11 p.m. during the experimental days;
 (7) Will be available and cooperate throughout the study duration.

Exclusion criteria are as follows:

Presence of cardiovascular disorders, hypertension, or diabetes; (2) Blood pressure above 120/80 mmHg and random blood glucose above 125 mg/dL; (3) Alcohol intake; (4) Smoking; and (5) Habitual coffee or tea drinkers.

Randomization

Participants who meet the eligibility criteria, possess medically acceptable vital signs, and submit a signed informed consent form will undergo randomization conducted by research staff. A simple randomization method will be employed. Each group will be assigned a distinct number, which will be inscribed on slips of paper corresponding to the total number of participants. Each slip, bearing one of the assigned group numbers, will be securely folded. These will then be put in a basket, which will be thoroughly jostled. All these procedures will be executed by a trained research personnel. Each participant will have the opportunity to randomly select one slip of paper. The selection process will be overseen by another research staff member who is not involved in the initial phase. The group number selected by each participant will determine their assigned group.

Compensation

At the end of the study, the participants will be compensated for cooperating and following through with all the research procedures. A token of one thousand naira will be given to each participant.

Safety considerations

This study involves healthy participants, and all the procedures involved in this study are generally safe, with minimal risks. To ensure the safety of the participants, all the parameters will be measured by well-trained and experienced research personnel. However, if any unfavorable or unintended sign or symptom arises, it will be noted as an adverse event. All research personnel will be trained to recognize, document, and report adverse events.

Follow-up

Although the study involves healthy participants and the study procedures are generally safe, the participants will be followed up via a phone call. All the participants will be requested to give their contact details and those of their family and friends. The follow-up call will be made twice (3 days and 10 days after the completion of the study). If an adverse event is recorded, a follow-up visit will be arranged with the participant to ensure their well-being.

Data management and quality control

To ensure protection of confidentiality, the data will be entered into the study database with no personal identity, and the source documents will refer to participants solely by their study identification number. Access to the data will be restricted to the research investigators. The study database will be securely stored in the central library of the University of Uyo and Faculty of Basic

Medical Sciences library. Additionally, all data will be compiled into a thesis that will not disclose any participant identities or information. Three copies of the thesis will be generated, which will be distributed as follows:

One copy will be submitted to the Faculty of Basic Medical Sciences library for preservation.

One copy will be retained in the Department of Physiology.

One copy will be kept in the University of Uyo library.

Ethics

All data collected during this study will be treated as strictly confidential. The personal information will be anonymized, and any published results will not include identifiable information. Participation in this study is entirely voluntary. The participants have the right to refuse to participate or withdraw from the study. The participants will consent to participate by filling out and signing an informed consent form. The protocol of this study will be submitted to the Akwa-Ibom State Health Research Ethics Committee, Ministry of Health, Akwa-Ibom State, Nigeria, for approval.

Statistical analysis

The results will be presented as mean \pm standard error of the mean (SEM). All data collected from the research will be analyzed using the Microsoft Excel (MS Excel) application and GraphPad Prism Software (Version 8.1). One-way and two-way analysis of variance (ANOVA), as well as Tukey's post-hoc comparison, will be used to determine the significant differences between the mean values. The statistical significance will be accepted at the level of P < 0.05.

Discussion

The role of diet in maintaining and promoting cardiovascular and metabolic health has long been a subject of scientific investigation and public interest. Among the diverse dietary components, coffee and tea have received attention for their potential health benefits. Their health advantages are primarily derived from their bioactive constituents, particularly polyphenols and caffeine. Honey, a natural sweetener, has been used for ages and has received attention for its ability to decrease blood pressure. It contains bioactive compounds such as flavonoids, which have vasodilating properties.

High blood pressure and elevated blood glucose level are significant risk factors for chronic diseases, including heart disease and diabetes. These conditions have become global health concerns, contributing to substantial morbidity and mortality. While pharmaceutical interventions are commonly used to manage these conditions, there is a growing interest in natural dietary approaches to support health. Coffee, tea, and honey both contain bioactive compounds that may influence blood pressure, blood glucose, and heart rate. Research on the possible health impacts of coffee, green tea, black tea, and honey has been done separately; however, there remains a notable lack of research examining the combined effects of these beverages with honey. This study protocol describes a randomized controlled trial designed to investigate whether a three-day consumption of either coffee, green tea, or black tea sweetened with honey can significantly change some physiological parameters in healthy young female adults.

This research aims to provide significant insights regarding the possible health benefits or risks linked to the consumption of coffee, black tea, green tea and honey-sweetened coffee, black tea,

and green tea. It will specifically focus on their effects on critical physiological factors such as blood pressure, heart rate, and blood glucose level. Understanding these factors is essential for maintaining individual health, as any adverse changes in them can lead to detrimental health consequences. By examining the relationship between these beverages and these vital health indicators, the study seeks to contribute to the broader understanding of dietary influences on cardiovascular and metabolic health.

References

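### The aim is acute and the objectives are three-day, the analysis is tied to neither, and post-drink readings alone cannot show an effect of three days' use beyond the cup just drunk

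*Combined protocol and SAP*

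**What the plan says.** Under Study goals and objectives, the Goals paragraph reads: "The primary aim of this study is to determine the effect of acute consumption of honey-sweetened coffee, black tea, and green tea". The first of the three objectives that follow is "To determine whether a three-day consumption of honey-sweetened black tea, green tea, and coffee will have an effect on blood pressure in healthy female individuals". The other two use the same form for heart rate and blood glucose. The Introduction and the Discussion also describe the question as one of three days' consumption.

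The exposure is set under Intervention: "The participants will be given a cup per day for 3 days". Study design describes 60 minutes of observation after the drink and adds: "This procedure will be repeated for the 3 days of the study". Under Study procedure, pre-drink values are taken after 30 minutes of rest: "This will serve as the 0-minute measurement". Blood pressure and heart rate are then "measured and recorded 15 minutes, 30 minutes, 45 minutes, and 60 minutes after consumption of the drinks", and "blood glucose levels of the subjects will be measured and recorded 30 minutes and 60 minutes after consumption".

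After day 3, the Follow-up section plans two phone calls, and a visit only if an adverse event is recorded. No outcome reading is planned there. The Statistical analysis section names one-way and two-way ANOVA with Tukey's comparisons. It does not give the factors, the day, the time point or the contrast that answers the aim or any objective.

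**The concern.** An acute effect is the response to the cup just drunk. An effect of three days' use could mean several things: the response on each of three days, a change in that response from day 1 to day 3, a shift in resting values, or the sum of these. The plan does not say which is meant, and different summaries of the same readings answer different versions.

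The risk lies in the conclusion. The Introduction itself describes caffeine as causing a short-lived rise in blood pressure. On that premise, a difference from water shortly after the third cup could arise even if the first two cups had left no trace. Nothing in the plan prevents that difference from being reported as an effect of three-day consumption. With the contrast unnamed, the choice between summaries could also be made after the data are seen.

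**Working it through.** The plan gives no figure to reproduce here, so the check is of which effects the schedule can estimate.

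**Inputs.** One cup a day for 3 days (Intervention). Readings at 0, 15, 30, 45 and 60 minutes for blood pressure and heart rate, and at 0, 30 and 60 minutes for glucose (Study procedure). Procedure repeated on each of 3 days (Study design). I first read the repetition as including the 0-minute reading; this is natural but not stated outright.

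**Count of time points.** Blood pressure and heart rate: 5 × 3 = 15. Glucose: 3 × 3 = 9.

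**What each reading estimates.** For a beverage group minus the water group, let c1, c2, c3 be the effect carried over after 1, 2 and 3 cups, free of the latest cup's acute effect. Let a1, a2, a3 be the acute post-drink response on days 1, 2 and 3.

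| Reading | Cups so far | Difference from water |
|---|---|---|
| Day 1, 0 min | 0 | 0 in expectation (randomised) |
| Day 1, post-drink | 1 | a1 |
| Day 2, 0 min | 1 | c1 |
| Day 2, post-drink | 2 | c1 + a2 |
| Day 3, 0 min | 2 | c2 |
| Day 3, post-drink | 3 | c2 + a3 |

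- c3 appears in no row. The number of readings after three cups and outside the third cup's 60-minute window is 0, so c3 cannot be estimated.
- Estimable: a1; c2 (day 3 pre-drink, after two cups); c2 + a3 (total effect on day 3); a3 − a1 (change in acute response); and (c2 + a3) − a1 (day 3 against day 1, post-drink values).
- If the 0-minute reading is taken on day 1 only, c2 and a3 − a1 are lost. The total c2 + a3 and the post-drink day-3 against day-1 comparison remain.

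**Why the choice of contrast matters (assumed values, mmHg relative to water).**

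- Carry-over of 4 with an acute response of 2 on day 3 gives 4 + 2 = 6 post-drink. Carry-over of 0 with an acute response of 6 also gives 6. The day-3 post-drink value alone cannot tell these apart.
- Carry-over of 0, 2, 4 before the drink on days 1 to 3, with a constant acute response of 6: the mean change from the same day's 0-minute value is (6 + 6 + 6)/3 = 6. Day-3 post minus day-1 pre is 4 + 6 = 10. Day-3 pre minus day-1 pre is 4.
- No carry-over and acute responses of 6, 4, 2: the mean over days is (6 + 4 + 2)/3 = 4, against 6 on day 1 and 2 on day 3.

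**Precision of the carry-over contrast** (day-3 minus day-1 0-minute value, one group against water). The Sample size section gives 70 participants, so 70/7 = 10 per group if equal. The within-person day-to-day SD, s, is not in the documents and is assumed to be 4 to 8 mmHg, with independent day-to-day deviations. SD of change = √2 × s; SE = SD of change × √(2/10); half-width = SE × t with 70 − 7 = 63 df, about 2.00.

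| s (mmHg) | SD of change | SE | 95% half-width |
|---|---|---|---|
| 4 | 5.7 | 2.5 | 5.1 |
| 6 | 8.5 | 3.8 | 7.6 |
| 8 | 11.3 | 5.1 | 10.1 |

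These are per-comparison intervals; Tukey's adjustment would widen them. The precision of a3 − a1 depends on how the 0–60 minute response is summarised, so it is not calculated here.

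**The case against.** The best defence is that the objectives ask only whether three days' consumption has an effect. They do not ask for a resting or cumulative effect free of the last cup. Day-3 post-drink values against a concurrent randomised water group estimate the total effect of the regimen, last cup included, and that fits the wording. This stands. A reader might infer that the objectives cannot be answered at all; the documents do not support that, because c2 + a3 is estimable.

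The two wordings can also be read together, with acute describing the response and three-day the period of exposure. That is possible, but the plan does not say so and the analysis section does not settle it.

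A reader might further infer that the plan pools the three days, or analyses change from the same day's 0-minute value, and so hides carry-over. The Statistical analysis section specifies neither. The numerical examples show only that the choice matters, not that a wrong choice has been made. Nor does habituation to the cuff and finger prick undermine the randomised comparisons, since the water group undergoes the same procedures.

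Finally, making day 1 alone the primary answer would set aside days 2 and 3. A defined average over the three days is also a legitimate acute quantity, so that choice belongs to the sponsor.

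**Conclusion.** The point holds as a question left undefined, with a limit on what may be concluded. The aim and the objectives differ, and no analysis is tied to either. No outcome reading follows three cups outside 60 minutes of the third. Post-drink comparisons with water give the acute effect or, on day 3, a total effect; alone they do not show an effect of three days' use beyond the cup just drunk. The day-3 pre-drink reading can address carry-over, but only after two cups and with a half-width of about 5 to 10 mmHg.

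This rests on three assumptions: that the 0-minute reading is taken daily; that a reading free of the acute effect means one outside the 60-minute window, since the documents do not say how long the acute effect lasts; and the SD range and equal groups used for precision. It should be fixed, but it does not invalidate the design, because randomised comparisons bearing on the stated objectives exist.

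**What to change.** 1. Reword the three objectives to match the acute primary aim: the 0–60 minute response to a cup, compared with Group 1. Name the day or days and the time points used. Day 1 alone or a defined average over days would both do; the sponsor should choose before the data are seen. Bring the matching sentences in the Introduction and Discussion into line.
2. State under Study procedure that the 0-minute reading is taken on each of the three days.
3. For repeated use, name two secondary contrasts, each as a difference from Group 1: the day-3 minus day-1 0-minute value, described as the effect after two daily cups; and the day-3 minus day-1 0–60 minute response.
4. Label any day-3 post-drink comparison as including the third cup's acute effect, and draw no three-day conclusion from post-drink values pooled over days.

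The cost is text in the objectives, procedure, analysis and discussion. No visit, reading or participant is added, provided the 0-minute reading is already meant to be daily; if it is not, pre-drink readings on days 2 and 3 are needed. The downside is a narrower and imprecise repeated-use claim. If the sponsor wants the effect of three cups free of the last one, these changes will not supply it: an outcome reading after the third cup's acute effect has passed would have to be added.

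### Fingertip glucose is sampled after an alcohol wipe alone, with no water wash or discarded drop, leaving open a one-sided error confined to the honey groups' post-drink readings

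*Combined protocol and SAP*

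**What the plan says.** The glucose procedure is in the protocol section Measurement of blood pressure, heart rate, blood glucose. The assay: "Blood glucose level will be measured by the oxidase method using a fine test glucometer". The preparation: "Firstly, the fingertip will be cleaned with an alcohol wipe and allowed to dry completely". After the prick: "The finger will be gently squeezed to help produce a small blood drop". Then: "Then the edge of the test strip will be used to touch the blood droplet until the meter beeps". The section mentions no washing with water and no wiping away of a drop, and it does not say which finger or hand to use. Blood pressure is read three times and averaged; no repeat reading is described for glucose.

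Under Methodology, honey is given in groups 3, 5 and 7 only, for example "2.25 g of coffee per 250 mL of hot water with 20 mL of honey". The Introduction describes honey as "primarily composed of carbohydrates, particularly in the form of monosaccharides like fructose and glucose". For the comparator, the Intervention section says: "The control group will be given 250 mL of water at 35°C".

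Under Study procedure, the baseline glucose is taken before the drink: "This will serve as the 0-minute measurement. The subjects will then be given the standardized drinks according to their groups". Glucose is measured again at 30 and 60 minutes, and under Study design the whole sequence is repeated on three days. Blood glucose is part of the primary aim and has its own objective.

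**The concern.** The outcome is read from a drop of blood on skin, and three of the drinks contain far more glucose per decilitre than blood does. If a trace of such a drink were on the lanced fingertip, it would mix with the drop and the meter would count it as blood glucose.

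The pattern of such an error matters more than its average size. Residue of the study drink cannot add sugar in the water or plain-drink groups, and it cannot be present at a 0-minute reading taken before that day's drink. It would act only upward, only in groups 3, 5 and 7, and only at 30 and 60 minutes. A real glycaemic effect of 20 mL of honey would be expected in the same groups, at the same times and in the same direction.

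Randomisation gives no protection, because the error would arise after allocation and from the drink itself. The one-way and two-way ANOVA with Tukey comparisons named under Statistical analysis could not separate the two effects. Adding baseline adjustment would not help, because the baseline is unaffected. More participants would only estimate the distorted difference more precisely. Both honey-versus-plain and honey-versus-water comparisons are exposed.

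**Working it through.** The plan gives no figure on this point, so there is nothing to reproduce. The check asks how little residue would matter.

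**From the documents:** 20 mL of honey per 250 mL drink; glucose at 0, 30 and 60 minutes on 3 days; 70 participants in 7 groups, so about 10 per group.

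**Assumed (not in the documents):** honey density 1.4 g/mL; 30-35% glucose by weight; 270 mL final volume (250 + 20); true blood glucose 90 mg/dL.

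**Glucose in the drink**
- 20 mL × 1.4 g/mL × 0.30 = 8.4 g; with 0.35, 9.8 g.
- 8,400 mg ÷ 2.7 dL = 3,111 mg/dL; 9,800 mg ÷ 2.7 dL = 3,630 mg/dL.

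**Rise in one reading.** If residue makes up a fraction p of the tested drop, the rise is p × (drink concentration − 90).

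| Residue, share of drop | Rise in that reading (mg/dL) | Shift in a group mean of 10 if one reading is affected (mg/dL) |
|---|---|---|
| 0 | 0 | 0 |
| 0.3% | 9.1-10.6 | 0.9-1.1 |
| 0.5% | 15.1-17.7 | 1.5-1.8 |
| 1% | 30.2-35.4 | 3.0-3.5 |

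The last column is the rise divided by 10.

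**Wider assumptions.** Take density 1.35-1.45 g/mL, 25-40% glucose and true glucose of 85 mg/dL.
- The drink holds 20 × 1.35 × 0.25 = 6.75 g to 20 × 1.45 × 0.40 = 11.6 g, or about 2,500-4,300 mg/dL.
- The share of the drop that adds 10 mg/dL is 10 ÷ (concentration − 85), which is 0.41% down to 0.24%.
- In volume terms, the rise is v × (concentration − 85) ÷ (V + v), for residue v in a drop V. A residue of 10 nL adds about 24-42 mg/dL to a 1 microlitre drop, but only about 5-8 mg/dL to a 5 microlitre drop. The protocol does not state the drop volume.

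**Readings exposed.** With equal groups, 30 honey participants × 2 post-drink readings × 3 days = 180, out of 70 × 3 × 3 = 630 glucose readings.

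The arithmetic shows that a very small residue would be enough to matter. It does not show that any residue is present, and the documents give no basis for choosing a value of p or a frequency.

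**The case against.** The strongest objection is that every link from the missing steps to an actual bias is assumed. Drink would have to reach a fingertip, on the finger that is lanced, still be there 30 or 60 minutes later, and survive the wipe. The documents show none of this. They describe the wipe as a cleaning step, assign measurements to trained staff, and have the honey added during preparation, so participants are not said to handle honey itself. This stands, and it rules out three stronger readings that a reader might draw.

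- *That the honey groups' glucose will be falsely raised.* The documents say nothing on how often residue occurs or how much sugar the wipe removes. The residue fractions above are illustrations, and the error is zero if the finger is clean.
- *That the plan instructs staff to test the first drop.* It does not. It only omits a discard step, so testing the first drop is a fair inference and no more.
- *That no other reading can be contaminated.* This holds only for residue of the study drink. Sugar from another source could be on any finger at any time, although the eligibility criteria restrict food and carbonated drinks.

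A second objection is practical. Washing at 30 and 60 minutes could disturb the seated rest between blood pressure readings. Requiring the hand that did not hold the cup could clash with the left-arm cuff. Both points are sound, and they shape the fix.

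The reach is also narrow: blood pressure, heart rate, glucose comparisons among the water and plain-drink groups, and the sample-size formula are all unaffected.

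What the objections do not remove is the asymmetry. If residue does occur, its effect cannot be told apart from a honey effect once the data are collected.

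**Conclusion.** The sampling procedure leaves open a possible differential measurement error of unknown frequency in an outcome named in the primary aim. The text supports its structure: a wipe is the only preparation described, honey is in three groups only, and baseline precedes the drink. Its size is conditional. Under the assumed honey composition, 270 mL of drink and true glucose of 90 mg/dL, residue of 0.3% of the drop adds about 9-11 mg/dL to a reading. The wider assumptions put the residue needed for a 10 mg/dL rise at 0.24-0.41% of the drop. Neither result is an estimate of bias in this trial. The case for acting is that the safeguard is very cheap and has to be in place before sampling.

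**What to change.** Amend the glucose paragraph in Measurement of blood pressure, heart rate, blood glucose so that the same steps apply in all seven groups on each study day:

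1. Participants clean their hands with water and dry them before the 0-minute sample, and again immediately after finishing the drink. The second cleaning is done at the seat and before the 15-minute reading, so that rest is not disturbed.
2. The alcohol wipe and full drying are kept before each prick.
3. At 0, 30 and 60 minutes the first drop is wiped away with dry gauze and the second is tested.

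No rule on which hand to use is needed, which avoids a conflict with the cuff arm. Applying the steps identically in every group and at baseline keeps the procedure from becoming a difference between groups.

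The cost is water, gauze and a minute or two per participant per day: 70 × 3 = 210 participant-days, or about 210-420 minutes over the whole study. No extra prick, test strip or participant is required.
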